8.2.2. Exclusion Criteria

1. Evidence of other malignant neoplasms (except nonmelanoma skin cancer or carcinoma in situ) within 5 years before switching to the sunitinib 2/1 schedule (all countries) or initiation of the 2/1 schedule (Brazil only).

8.3. Variables

All measures/variables will be gathered from existing medical records using the eCRF. In the following sections, we describe the key analysis variables and study measures that will be gathered directly through the eCRF or constructed during analysis.

8.3.1. Patient Characteristics

Demographic characteristics available in patients' medical records will be documented, including, but not limited to, the following (when available):

- Sex;
- Year of birth;
- Primary health insurance type (eg, supplemental private insurance, uninsured), if relevant;
- Comorbidities (eg, hypertension, diabetes);
- Height;
- Weight;
- Body mass index.

8.3.2. Baseline Clinical Characteristics

A number of clinical characteristics related to the initial RCC diagnosis and diagnosis of metastatic RCC will be collected. These characteristics may include, but are not limited to, the following (when available):

- Dates of diagnosis of initial (if first diagnosed at an earlier stage) and metastatic RCC;
- Stage of RCC at the time of initial diagnosis;
- Tumor grade at the time of initial diagnosis;

[figure not shown]
- Risk group at the time of initial diagnosis (eg, Memorial Sloan Kettering Cancer Center [MSKCC], International Metastatic Renal Cell Carcinoma Database Consortium [IMDC]);
- Site(s) of distant metastases at the time of initiation of first-line treatment with sunitinib and at the switch;
- Performance status (eg, Eastern Cooperative Oncology Group [ECOG], Karnofsky Performance Status Scale) at the time of initiation of first-line treatment with sunitinib and at the switch.

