7. RESEARCH QUESTION AND OBJECTIVES

This study consists of compiling and analyzing recent data from a customized retrospective medical record review conducted in 7 countries (Argentina, Brazil, Colombia, Costa Rica, Ecuador, Mexico, and Peru) to assess the following primary objectives:

- Describe demographic and clinical characteristics of patients in Latin America diagnosed with metastatic RCC who received first-line sunitinib and switched from the 4/2 to the 2/1 schedule.
- Characterize detailed first-line sunitinib treatment patterns, including dose, schedule, total duration of sunitinib treatment, duration on the 4/2 schedule, duration on the 2/1 schedule, reasons for stopping treatment lines, and supportive care.

The secondary objectives of the study will include an exploration of clinical outcomes (ie, response to treatment, AEs, PFS, and overall survival) after switching to the 2/1 schedule. Switching to the 2/1 schedule is a relatively new occurrence in the studied countries, resulting in limited available follow-up time to observe clinical outcomes among patients who switched to the alternative schedule. Furthermore, this study relies on a convenience sample of sites treating patients at a select number of treatment centers, will provide only descriptive information on observed events, and is designed to generate, not test, hypotheses. In Brazil, early feasibility results suggest physicians frequently prescribe sunitinib on the 2/1 schedule at first-line initiation; therefore, secondary objectives will also include a descriptive exploration of demographic, clinical and treatment characteristics (eg, duration of treatment, reasons for stopping treatment), and clinical outcomes (eg, treatment response, AEs, PFS, and overall survival) among patients initiating first-line sunitinib on the 2/1 schedule. It is anticipated this sample will be relatively small. Secondary objectives will be assessed with known limitations concerning data availability and generalizability of the findings.

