8. RESEARCH METHODS

[figure not shown]
To achieve the study objectives described in Section 7, PPD, a research consultancy specializing in conducting multinational real-world health economic and outcomes studies, will analyze retrospective medical record data from 150 patients who received care at treatment centers across 7 Latin American countries. Prior to initiation of data collection activities, PPD, in consultation with Pfizer Inc. (Pfizer), will develop a customized case report form (CRF) to capture detailed data on demographics, clinical characteristics, treatment patterns, AEs, and health outcomes from eligible patients' medical records. The length of the CRF will be consistent with an abstraction time burden of approximately 30 to 45 minutes. After selection of potential sites by Pfizer, PPD will work with the sites to assess feasibility of the site's participation by using a site information form. If the study is determined to be feasible at a specific site, the principal investigator (PI) and their designated research team at the participating site will obtain the necessary ethics approvals for conducting this study. In countries where national ethics activities are required, a lead site in the relevant country will be selected to support the national

submission. Specific responsibilities to be conducted and coordinated by Pfizer, PPD, and individual sites during the site identification, feasibility assessment, contracting process, and data collection are shown in Figure 1.

Following receipt of the required ethics approvals, the site PI and/or designated research team will be provided a link(s) to the secure electronic CRF (eCRF) to enter the abstracted data electronically. The PI may personally abstract data and/or designate their research team to abstract data. Once a potential medical record is identified, the abstractor will answer multiple screening questions in the eCRF to confirm the selected medical record is eligible for inclusion. Next, the abstractor will complete the eCRF by retrospectively reviewing all available data in the patient's medical record.

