8.2.1. Patient Inclusion Criteria

1. Diagnosed with metastatic RCC with clear cell histology:
 - a. The patient may have been initially diagnosed with Stage IV or initially diagnosed at an earlier stage and progressed to having disease at distant sites (ie, metastatic disease).
2. Initiated first-line treatment for metastatic RCC with sunitinib on the 4/2 schedule (all countries) or initiated first-line treatment for metastatic RCC with sunitinib on the 2/1 schedule (Brazil only).
3. Switched to the 2/1 schedule (all countries) or initiated the 2/1 schedule (Brazil only) during the first treatment line between January 1, 2014, and June 30, 2018:
 - a. The final dates defining this selection period will be dependent on country-specific ethics and reporting requirements.
4. Aged 18 years or older at the time of the switch to the 2/1 schedule (all countries) or initiation of the 2/1 schedule (Brazil only).

PFIZER CONFIDENTIAL

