8.3.4. Treatment-related Outcomes

Treatment-related AEs (eg, hypertension, neutropenia, thrombocytopenia, fatigue, stomatitis) will be documented for the duration of first-line treatment with sunitinib. Frequency of toxicity evaluation (eg, every 6 weeks) and the method of evaluation (eg, radiological evaluations by computed tomography, magnetic resonance imaging with measurable lesions via Response Evaluation Criteria in Solid Tumors [RECIST]) will also be documented.

Dates of progression and death (ie, whether the patient died during the follow-up period and whether the death was related to RCC) will be documented. Disease progression and survival estimates will be derived from these measures and calculated from the date of diagnosis of metastatic RCC, the start of first-line treatment line with 4/2 or 2/1 sunitinib, and the time of switch to the 2/1 schedule (among those who initiated on the 4/2 schedule). Survival estimates will include, but are not limited to, the following:

[figure not shown]
- Overall survival;
- PFS;
- Time to second-line initiation.

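### Risk group is recorded at initial RCC diagnosis, which for patients first diagnosed before metastasis says nothing about prognosis at sunitinib start and matches no PFS or OS time origin

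*Combined protocol and SAP*

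**What the plan says.** Section 8.3.2 of the protocol lists the baseline clinical characteristics to be abstracted. The risk-group item reads "Risk group at the time of initial diagnosis (eg, Memorial Sloan Kettering Cancer Center [MSKCC", with IMDC as the second example. Stage and tumor grade carry the same timing. The list opens with "These characteristics may include, but are not limited to, the following (when available", so it is neither closed nor mandatory.

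The same list treats initial and metastatic diagnosis as separate events: "Dates of diagnosis of initial (if first diagnosed at an earlier stage) and metastatic RCC". Its last two items are timed differently from risk group. Sites of distant metastases are recorded at the start of first-line sunitinib and again at the switch, and so is "Performance status (eg, Eastern Cooperative Oncology Group [ECOG], Karnofsky Performance Status Scale) at the time of initiation of first-line treatment with sunitinib".

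Inclusion criterion 1a (section 8.2.1) accepts patients with Stage IV disease at first diagnosis and also those "initially diagnosed at an earlier stage and progressed to having disease at distant sites". In section 8.3.4, progression and survival are "calculated from the date of diagnosis of metastatic RCC, the start of first-line treatment line with 4/2 or 2/1 sunitinib", and also from the switch to the 2/1 schedule for patients who began on 4/2.

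The first primary objective in section 7 is to "Describe demographic and clinical characteristics of patients in Latin America diagnosed with metastatic RCC who received first-line sunitinib" and switched schedule.

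**The concern.** A baseline prognostic variable should describe the patient at or near the point where the treatment of interest begins. Here that point is the start of first-line sunitinib for metastatic disease. For a patient first diagnosed with localized disease, a risk group at initial diagnosis belongs to an earlier stage of the illness. IMDC, by the name spelled out in the list of abbreviations, concerns metastatic RCC.

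For such a patient the abstractor has three options: enter a group that pre-dates metastasis, leave the field empty, or enter a later group under the wrong label. If sites differ in what they do, one variable will hold several time points. Section 8.3 lists no date for the risk assessment, so the mixture might not be visible in the data.

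At stake is the description of the cohort. Section 6 links first-line treatment options to prognosis, and hopes the study will show which kinds of patients may benefit from the alternative schedule and supply baseline measures for later comparison. A risk-group distribution that does not refer to sunitinib start serves neither use for the affected patients. The limitations in section 8.9 do not mention this.

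**Working it through.** The plan gives no figure to reproduce: section 8.5 states that no power calculation was done. The check sets the timing of the variable against eligibility and against the time origins.

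**Step 1. Can initial diagnosis be read as metastatic diagnosis?** The first item in section 8.3.2 gives the two separate dates when the patient was first diagnosed at an earlier stage. Stage and grade carry the same timing words as risk group, and stage at that point varies between patients only if it is not always Stage IV. The plain reading is first diagnosis of RCC at any stage.

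**Step 2. Are affected patients in the study?** Yes, by criterion 1a. Section 8.3.3 also collects neoadjuvant treatment, surgery and adjuvant therapy given before metastatic diagnosis, so the plan expects them.

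**Step 3. Is risk group scheduled anywhere else?** No section places it at metastatic diagnosis, sunitinib start or the switch.

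**Step 4. Compare with the origins in section 8.3.4.** The table applies to patients who switched from 4/2 to 2/1.

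| Time origin for PFS and OS | Equals initial diagnosis, first diagnosed earlier | Equals initial diagnosis, Stage IV at diagnosis |
|---|---|---|
| Metastatic diagnosis | No | Yes |
| Start of first-line sunitinib | No | Not by definition |
| Switch to 2/1 | No | No |
| Total | 0 of 3 | 1 of 3 |

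The switch does not apply to the Brazilian patients who started on 2/1, so their counts are 0 of 2 and 1 of 2.

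**Step 5. How many records?** The share first diagnosed before Stage IV is not in the documents, and logically it could lie anywhere from 0% to 100%. Against the target of at least 150 records:

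- per 10 percentage points: 0.10 × 150 = 15 records
- at 90%: 0.90 × 150 = 135 records

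The range of 15 to 135 records is a conversion scale for an assumed share of 10% to 90%. It is not an estimate.

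**The case against.** The strongest reply is that the binding document has not been seen. The list in section 8.3.2 is open and depends on availability. Section 8 says the contractor "will develop a customized case report form (CRF) to capture detailed data on demographics, clinical characteristics" and other items, and section 8.7 defers detailed methods to a separate statistical analysis plan that is not in the supplied text. The eCRF may already fix a sensible date, and initial diagnosis may be loose wording for first diagnosis of metastatic disease. An open list allows additions, but it does not correct the one time point it names, and the loose reading conflicts with the list's own first item. What stands is that the eCRF must be checked, and that entry of different time points by different sites is a possibility the documents do not demonstrate.

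Second, no planned analysis uses risk group. Section 8.7 describes outcomes without comparing schedules, and allows up to two subgroups chosen after data review, with number of 4/2 cycles as the example. This stands and limits the consequence to cohort description and to reading the survival curves. In a descriptive study, though, the baseline description is itself a main result.

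Third, moving the item to sunitinib start also guarantees only one of the three origins for switchers. That is correct. For Stage IV patients the count stays at one; for the others it rises from none to one. The better argument for that time point is that it marks the start of the treatment under study and is already used for the neighbouring variables.

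Fourth, the gain depends on what was charted, and the list names no laboratory values from which a group could be derived. This also stands. It is a cost of the fix, although every item is already collected only when available.

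**Conclusion.** The concern holds. As written, section 8.3.2 asks for a risk group that, for patients first diagnosed before metastasis, pre-dates metastatic disease or does not exist. It coincides with none of the origins used for PFS and OS. Patients with Stage IV disease at diagnosis are affected at sunitinib start only if treatment was delayed.

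The consequence is confined to one row of the baseline table and to the interpretation of outcomes beside it. Correctly timed performance status and metastatic sites soften it. The number of patients involved is unknown. The conclusion rests on the plain reading of initial diagnosis and on the eCRF following the listed timing, which cannot be confirmed from the documents. This is a correction that should be made, but not one that threatens the study.

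**What to change.** Retime the item in section 8.3.2 to: *Risk group (e.g. MSKCC, IMDC) at start of first-line sunitinib*. This wording covers both the switch sample and the Brazilian 2/1 sample. Leave stage and tumor grade at initial diagnosis, where they belong. Recording the group at the switch as well is optional, where it is already charted. Check that the eCRF field and its label carry the same timing.

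The change should precede abstraction. Under section 8.6.7 neither the sponsor nor the contractor can see the medical records, so a later correction would have to go back to the sites.

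The cost is one protocol line and, if it carries the same timing, one eCRF field. Abstractors will need slightly more look-up within the planned 30 to 45 minutes per record, and values will be missing where no group was charted at sunitinib start. Those gaps should be reported as missing and not filled from an earlier date.

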8.3.3. Treatment Patterns

Measures related to the treatment of RCC before (if applicable) and after diagnosis of metastatic RCC will be gathered. [Figure 2](#) graphically depicts the time periods during which treatment patterns will be assessed for each sample. Treatment measures may include the following:

- Receipt of broad categories of treatment approaches, including neoadjuvant treatment(s), surgery, and adjuvant therapy before the diagnosis of metastatic RCC:
 - Date of receipt of last cancer-direct treatment before the diagnosis of metastatic RCC.
- Total number of systemic lines of treatment after the diagnosis of metastatic RCC:
 - Start and stop dates of each treatment line (duration of each treatment line will be calculated).
- Specific details regarding first-line treatment with sunitinib after the diagnosis of metastatic RCC include the following (where relevant to the specific sample):
 - Start and stop dates of the 4/2 schedule (duration of 4/2 treatment);
 - Date of switch to or initiation of the 2/1 schedule and stop date (duration of 2/1 treatment);
 - Time between stopping the 4/2 schedule and initiating the 2/1 schedule;
 - Reason for switch to 2/1 schedule;
 - Date of subsequent changes in schedule, if any
 - Reason for subsequent changes in schedule, if any
- Initial and subsequent daily dose(s) of sunitinib on the 4/2 and 2/1 schedules:
 - Date(s) of dose change(s), if applicable;

PFIZER CONFIDENTIAL

- Reason for change(s) in dose, if applicable.
- Reason for stopping treatment with sunitinib (eg, AE, progressive disease);
- Best clinician assessed response to treatment with sunitinib on the 4/2 schedule and best response on the 2/1 schedule.
- Receipt of broad categories of supportive care elements (medications and procedures) such as nutritional supplements, pain medications, antibiotics, antifungals, iron supplements, antiemetics/antinauseants, antidiarrheals, antivirals, radiation therapy, bone-targeting agents (eg, bisphosphonates, denosumab), erythropoiesis-stimulating agents, granulocyte-colony stimulating factors, folic acid, red blood cell transfusion, and platelet transfusion during the first line of treatment with sunitinib.

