1. Explore clinical outcomes after switching to the 2/1 schedule, including response to treatment, AEs, progression-free survival (PFS), and overall survival.
2. Describe demographic, clinical and treatment characteristics (eg, duration of treatment, reasons for stopping treatment), and clinical outcomes (eg, treatment response, AEs, PFS, and overall survival) among patients in Brazil who initiated first-line sunitinib treatment for metastatic RCC on the 2/1 schedule.

Study Design: Noninterventional, retrospective medical record review of patients with metastatic RCC who received first-line treatment with sunitinib and switched from the 4/2 to 2/1 administration schedule. A second sample of patients who initiated first-line treatment with sunitinib on the 2/1 schedule in Brazil will be collected and analyzed separately.

Population: Patients diagnosed with metastatic RCC with clear cell histology who switched from a 4/2 schedule to a 2/1 schedule of sunitinib in first-line metastatic treatment between January 1, 2014 and June 30, 2018. Patients must be aged 18 years or older at the time of the switch. The final dates defining this selection period will be dependent on country-specific ethics and reporting requirements. A second sample of adults who initiated first-line treatment with sunitinib on the 2/1 between January 1, 2014 and June 30, 2018 in Brazil will be collected and analyzed separately.

Variables: Patient characteristics, clinical characteristics, first-line treatment patterns, treatment-related outcomes, AEs, and survival.

Data Sources: Information will be abstracted from patients' medical records and compiled into an anonymized analytic database. All abstracted information will be retrospective.

Study Size: Data will be abstracted from a target of at least 150 medical records of patients treated at various sites across 7 Latin American countries.

[figure not shown]

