8.7. Data Analysis

All measures described in [Section 8.3](#) will be summarized descriptively through the tabular and graphical display of mean values, medians, ranges, and standard deviations of continuous variables of interest and frequency distributions for categorical variables. Time-to-event outcomes (ie, overall survival, PFS, time to second-line initiation) will be described using the Kaplan-Meier method. All analyses will be conducted using SAS (version 9.4 or later) statistical software. Samples of patients who switched from the 4/2 to the 2/1 schedule from each country will be pooled and analyzed in aggregate. The sample of patients from Brazil who initiated first-line sunitinib on the 2/1 schedule will be analyzed separately. Results may be described for up to 2 subgroups that will be determined after the initial review of the data (eg, number of cycle on the 4/2 schedule).

As this study is descriptive and designed to generate hypotheses, direct comparisons between outcomes on the 4/2 schedule and on the 2/1 schedule will not be conducted. Potential confounders, such as characteristics that prompt the switch and other possible time-dependent factors (eg, dose modifications and delays), are not comprehensively collected or controlled for in this study design. Variability in timing of the switch from a 4/2 to a 2/1 schedule will affect the distribution of time-dependent outcomes after the switch (even in the absence of immortal-time bias), as some patients may switch “early” in their first-line therapy and others may switch “later.” Thus, causal inferences about the benefit of switching treatment schedules cannot be drawn.

PFIZER CONFIDENTIAL

Detailed methodology for summary and statistical analyses of data collected in this study will be documented in a statistical analysis plan, which will be dated, filed and maintained by the sponsor. The statistical analysis plan may modify the plans outlined in the protocol; any major modifications of primary endpoint definitions or their analyses would be reflected in a protocol amendment.

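### For patients who switch from 4/2 to 2/1, best response on 2/1 is tabulated with no reference assessment and no separation of responses first reached on 4/2

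*Combined protocol and SAP*

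**What the plan says.** Section 8.3.3 lists among the treatment measures: "Best clinician assessed response to treatment with sunitinib on the 4/2 schedule and best response on the 2/1 schedule". Each switcher can thus contribute two best-response values.

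Section 7 gives as a secondary objective "an exploration of clinical outcomes (ie, response to treatment, AEs, PFS, and overall survival) after switching to the 2/1 schedule"; the Abstract says the same.

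Section 8.7 states that the Section 8.3 measures "will be summarized descriptively through the tabular and graphical display of mean values, medians, ranges, and standard deviations of continuous variables of interest", with "frequency distributions for categorical variables". It leaves detailed methods to a separate statistical analysis plan.

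The switch takes place within one treatment line. Section 8.2.1 requires that the patient "Switched to the 2/1 schedule (all countries) or initiated the 2/1 schedule (Brazil only) during the first treatment line". On the second sample, Section 8.7 says: "The sample of patients from Brazil who initiated first-line sunitinib on the 2/1 schedule will be analyzed separately".

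Sections 8.7 and 8.9 rule out causal conclusions about switching, and 8.7 also rules out direct comparison of the two schedules. Both sections warn that the timing of the switch varies and affects time-dependent outcomes. Neither mentions response carried over from 4/2.

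**The concern.** A switcher takes the same drug before and after the switch. A tumour that has already shrunk on 4/2 may still meet the definition of response at the first assessment on 2/1. If the clinician judges against the pre-sunitinib scan, that patient can be recorded as a responder on both schedules, although nothing new happened on 2/1. If the clinician judges against a scan at the switch, the same patient may be recorded as having stable disease on 2/1. The plan does not say which applies, so one column of 2/1 frequencies can contain either kind of entry, or both.

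What is at stake is the reading of one named secondary outcome. A reader of a stand-alone 2/1 response rate cannot tell how many patients first responded after switching, how many had already responded and how many got worse. The primary objectives are not affected.

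**Working it through.** There is no planned figure to reproduce. The target of at least 150 records (Section 8.5) has no power calculation behind it, and no response rate is given for either schedule as used in this study. The point is mainly one of definition, so the first step is to read the sections together.

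**What the text fixes and what it leaves open**

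- *Reference point.* Section 8.3.4 gives progression and survival explicit time origins: metastatic diagnosis, start of first line, and the switch. Response in 8.3.3 has none.
- *Assessment.* Section 8.3.4 records the method of evaluation, with imaging and RECIST as examples, but not the baseline scan.
- *Status at the switch.* Section 8.3.2 records metastatic sites and performance status again at the switch. Response status at the switch is not listed.
- *Dates.* Section 8.3.4 dates progression and death. A date of response is not listed.
- *Who is exposed.* Only patients with a 4/2 period before 2/1. The Brazil 2/1 initiators have no earlier schedule from which a response could carry over.

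**Illustration (all rates assumed)**

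Let r1 be the share already in response at the switch, m the share of those still recorded as responders on 2/1, and r2 the new-response rate on 2/1 among the rest. For simplicity this treats 4/2 best response as status at the switch, and all 150 patients as switchers.

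- Apparent 2/1 rate = r1·m + (1 − r1)·r2
- New responses among all patients = (1 − r1)·r2
- Carried-over share of 2/1 responders = r1·m / [r1·m + (1 − r1)·r2]

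*One case:* r1 = 20%, m = 100%, r2 = 10%.

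- Carried over: 150 × 0.20 = 30. New: 120 × 0.10 = 12.
- Apparent rate: 42/150 = 28%.
- New responses: 12/150 = 8% of all patients, or 12/120 = 10% of those not in response at the switch.
- Carried-over share: 30/42 = 71%.

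*Range:* r1 10–30%, m 70–100%, r2 5–20%.

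- Apparent rate: from 0.10 × 0.70 + 0.90 × 0.05 = 11.5% to 0.30 × 1.00 + 0.70 × 0.20 = 44%.
- Carried-over share: from 0.07/(0.07 + 0.18) = 28% to 0.30/(0.30 + 0.035) = 90%.

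*Re-baselining at the switch:* keep the first case, but let all 30 maintained responses be recorded as stable disease (m = 0, outside the range above). The 2/1 rate becomes 12/150 = 8%. The same patient histories therefore give 28% or 8%, depending on a rule that is not written down. For scale, the 95% half-width for a proportion of 30% in 150 patients is 1.96 × √(0.30 × 0.70/150) = 7.3 percentage points.

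*Is the 2/1 rate bound to be at least the 4/2 rate?* No. With r1 = 30%, m = 70%, r2 = 5%, it is 0.21 + 0.035 = 24.5%, below 30%.

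**The case against.** The strongest reply has four parts.

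1. *The study disclaims the reading that would do harm.* It is descriptive, makes no direct comparison of schedules and draws no causal conclusion. This stands and limits the consequence. It does not define the variable: even with no comparison, the 2/1 figure alone mixes kinds of response that a reader would want separated.

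2. *Best response while on 2/1 is a legitimate description.* The objective speaks of response to treatment after switching, not of new response, and a maintained response is relevant for a schedule proposed as better tolerated with similar outcomes. This also stands. A reader might infer that the 2/1 distribution is invalid or cannot describe the period after the switch; the documents do not support that. It is incomplete alone.

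3. *Nothing forbids a cross-tabulation, and the detail may come later.* Section 8.7 does not confine itself to one-way tables, and neither the separate statistical analysis plan nor the finished CRF is part of the document reviewed. Either could supply the rule. That is a reason to make sure it is written before abstraction starts, since the reference assessment may be hard to recover afterwards.

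4. *The paired table is imperfect.* A patient may respond on 4/2 and lose the response before switching, so 4/2 best response is not status at the switch. The table cannot tell a maintained response from a regained one. This stands and belongs in the limitations.

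**Conclusion.** The concern holds for switchers only. The plan gives no reference assessment for best response on 2/1 and does not separate responses first reached on 4/2, so the 2/1 rate does not by itself show what happened to response after switching.

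A reader might go further and infer that maintained responses are counted as 2/1 responses, so that the 2/1 rate is inflated and will match or exceed the 4/2 rate by construction. The documents do not support this. They state no counting rule. Re-baselining would push the error the other way, and even when earlier responses are counted, imperfect retention can put the 2/1 rate below the 4/2 rate.

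The size cannot be stated. The carried-over share of 28–90%, and the contrast between 28% and 8%, rest wholly on assumed rates. They show only that the missing rule can matter. The change is still worth making, because a paired table is more informative than a stand-alone distribution and uses two items already listed for collection on each switcher.

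**What to change.** - **Section 8.7, switchers only.** Report best response on 2/1 cross-tabulated by best response on 4/2. Show the number with a 2/1 response among patients without a response on 4/2, separately from those who had already responded on 4/2, and show those whose category worsened. Present this as description only, with no test. The Brazil 2/1 initiators keep a simple distribution, since they have no 4/2 response.
- **eCRF.** Add one item asking whether the recorded 2/1 response was judged against the pre-sunitinib assessment or an assessment at the switch. Section 8.4 has the eCRF programmed while ethics review is under way, so the item can be in place before abstraction.
- **Section 8.9.** State that best response on 4/2 is not the same as response status at the switch.

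The cost is one extra table, some of whose cells will be small, and one eCRF item. No additional patients are needed.
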